6.8.2 Control group

The control group will continue receiving standard care in the hospitals. The control group shall receive a reminder text messages one day before the routine clinic appointment. The clinic appointment dates shall be derived from the hospital where the participant receives routine diabetes care.

Figure 3 describes the study timeline and workflow. At the beginning of the intervention, both the control and intervention groups will receive introductory text messages. Text messages shall consist of personalized salutation (using the preferred name of the participant) sent to the officially registered mobile numbers. The messages shall be sent between 10am and 3pm through the Africa’s Talking® Application Programming Interface (API).

[figure not shown]

Figure 3. Study timeline

Table 2. Text messages for specific target behaviors

COM-B Components	What needs to happen for the target behavior to occur?	Behavior Change Technique	Text No	Text Messages	
Physical capability	Be able to select healthy food	Instructions on how to perform behavior	S 1	To meet nutrient needs within calorie limits, choose a variety of nutrient-dense foods across and within all food groups in recommended amounts. Energy dense foods include vegetables, fruits, whole grains, beans, nuts and seeds, and lean protein — when prepared with little or no saturated fats, added sugars and sodium	
			S 2	There are 5 food groups: (1)Vegetables and legumes or beans (2)Fruit; (3)Lean meats and poultry, fish, eggs, nuts and seeds, legumes or beans;(4) Grain (cereal) foods, mostly wholegrain or high cereal fiber varieties (5) Milk, yoghurt, cheese or alternatives, mostly reduced fat.	
			S 3	Reduce foods and beverages that are high in added sugars to better control your blood sugar. To avoid added sugars, check for words like brown sugar, corn sweetener, corn syrup, dextrose, fructose, and high-fructose corn syrup. These are added sugars	
			S 4	Reduce or avoid foods and beverages that are high in saturated fat like whole milk, cream, butter, cheese, meat, palm oil and coconut oil. Instead, select low-fat milk and use healthier plant-based oils.	
			S 5	Instead of selecting canned fruit or bottled juices, buy fresh juice or fruits as they are energy dense and have fiber that helps in blood sugar control. Fresh fruits are also cheaper.	

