	Be able to eat healthy food diet			E1	To ensure you eat a healthy diet, try to eat the following food servings most days of the week: (1) Vegetables and legume beans: Like 5-6 medium cups of managu, or mixed vegetables, or 2 tomatoes. (2) Fruits: Like 2 medium size apples, bananas, oranges or pear. (3)Lean meats and poultry, fish, eggs, nuts and seeds, legumes or beans: Like 200g raw meat or fish, or 2 eggs, or 60g of nuts or 300g beans ; (4) Whole meal grain (cereal) foods: Like 60–90 g of Ugali, bread, chapati (5) Milk, yoghurt, cheese or alternatives: like 500 ml milk or yoghurt
				E 2	Most processed carbohydrate foods release glucose more quickly than whole grain carbohydrates. Eat whole grain carbohydrates which produce a slower rise in blood glucose levels, which are called low-glycemic index (GI) foods and result in better blood glucose control.
				E 3	Low GI foods include some posho milled unga, high-fiber breads and whole meal cereals githeri, most fruits, legumes, and low-fat dairy products
				E 4	Eating vegetables before a carbohydrate rich meal has been shown to have beneficial effects on blood sugar levels. This practice slows down the speed at which carbs are absorbed into the bloodstream and may benefit both short- and long-term blood sugar control.

			E 5	Eat fruits instead of making fruit juice. Fruits contain fiber and various plant compounds. Sugar from fruits is generally digested very slowly and do not cause increases in blood sugar levels.		
			E 4	Limit pork, lamb, beef meats: instead, eat plant-based proteins like beans, green peas, green grams or animal proteins like eggs or fish. Pork, lamb, beef meats contain saturated fats		
			E 6	Limit lard/bacon /chicken fat/butter, instead, vary with liquid vegetable-based oils: Use olive oil or vegetable oil for cooking. Limit lard, bacon, chicken fat and butter contain saturated fats		
			E 7	Eat regular meals and spread out your servings of energy giving foods evenly throughout the day. This helps you can maintain energy levels without causing large rises in blood glucose levels.		
Psychological capability	Know healthy food	Information about health consequences	S 6	The amount of carbohydrate in your meal has the greatest effect on blood glucose levels. Avoid big servings of carbohydrates in your meal and ensure most of your energy giving foods are composed of whole meal or high fiber. Make vegetables and fruits take the larger portion of your plate.		

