			S 7	There are two main types of fat: saturated and unsaturated. Too much saturated fat in foods like fatty meat, sausages and butter can increase the amount of cholesterol in the blood, which increases your risk of developing heart disease.		
			S 8	Instead of selecting foods with saturated fats, select foods with unsaturated fats like nuts, seeds, seafood, and avocados.		
			Advanced planning skills to ensure selection of food healthy food		S 9	Some food items like sauces have hidden sugar and salt, therefore it is wise to avoid tomato sauces, fat-free salad dressings, and condiments. Instead of sauces. To improve the taste of your food, select preferred spices, herbs, onions, or other low-energy flavorings
				S 10	Select whole or minimally processed foods, which help to control your blood glucose	
				S 9	Make an eating plan each week – this is the key to fast and easy meal preparation. This will also ensure that you plan for healthy diets and better controlled blood glucose.	
				S 11	Plan to have meals with plenty of vegetables and fruit. Your goal is to fill half your plate with vegetables and fruit at every meal. Choose colored fruits like oranges, mangoes, loquats, plums and vegetables like managu, carrots and tomatoes.	
	Know the composition of the plate model		E 8	Start with a 9-inch dinner plate Fill half with non-starchy vegetables, such as managu, Sukuma wiki , green beans, broccoli, cauliflower, cabbage, and carrots. Fill one quarter with a lean protein, such as chicken, fish, legumes or beans, or eggs. Fill one quarter with whole meal carbohydrate foods: grains, starchy vegetables (such as potatoes and peas), rice, pasta, beans, fruit, and yogurt. A cup of milk also counts as a carb food.		
Social Opportunity	Change cultural habits on portion size	-Goal setting (behavioral) -Restructuring the physical environment	S 12	Controlled portion sizes of food are important to reducing calorific intake. To control your portion sizes, plan to use a smaller plate size when serving meals.		
			S 13	Your health is a personal responsibility. When eating, try to avoid places that may entice you to eat excessive food. Eat most of your meals at home for better control of healthy food and your blood sugar		

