Reflective motivation	Intend to select healthy diet	-Information about health consequences -prompts/cues	S 14	Make your shopping list ahead of time and do not go shopping while hungry. This helps you to buy healthier items but also save money and select healthier foods.
			S 15	Intend to purchase less saturated and unhealthy fats by using oils like canola, corn, olive, peanut, safflower, soybean, and sunflower oils. Unsaturated oils that are healthy and are also naturally present in nuts, seeds, seafood, and avocados.
			S 16	Intend to select healthy dietary pattern by selecting foods and beverages that have low or no added sugars, saturated fat, and/or sodium. Check food labels to check the nutrient content of the food items.
			S 17	Instead of purchasing processed grade 1 flour or unga, use posho mill unga. It contains fiber and other plant extracts that are important to the body and blood sugar control.
	Intend to prioritize eating healthy diet		E 9	Small changes to more nutrient-dense, single food and beverage choices combine to become a nutrient dense meal, and can lead to a whole day made up of nutrient-dense meals and snacks, increasing you blood sugar control
			E 10	Place fresh and locally available low-carbohydrates fruits on the table or where they are easy to reach to increase intake of fruits. This enables you to eat healthy and avoid unhealthy snacking.
			E 11	To reduce salt intake, ensure that salt is added to food when cooking. Avoid having saltshakers on the table when eating
			E 12	A supportive family enables you to eat healthy meals. Enlist your family members to support you to encourage your intake of healthy meals by planning meals and eating together.
			E 13	Portion sizes of food affect the calories consumed. Plan to control your portion sizes by using smaller plates and ensuring that you apply the plate model in serving your various foods
			E 14	Water is important to prevent dehydration and aid in the digestion of food and absorption of nutrients. To increase water intake, flavor your water with fruits like lemon or orange.

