Automatic motivation	Establish routines and habits to select healthy diet	Instructions on how to perform behavior	S 18	Keep a food diary for a few days to evaluate what you eat every day. Note how you were feeling when you ate – hungry, not hungry, tired, or stressed? Create a list of “cues” by reviewing your food diary to become more aware when you’re “triggered” to eat for reasons other than hunger. Is there anything else you can do to avoid the cue or situation? If you cannot avoid it, do something differently that would be healthier. Replace unhealthy habits with new, healthy ones
			Restructuring the physical environment Prompts/Cues	S 18
			E 15	Eat smaller meals more often. Eat at least three meals a day with snacks in between. When you wait too long to eat you are more likely to make unhealthy food choices.

	Establish routines and habits to serve and eat healthy diet		E 16	Make a routine of eating healthy snacks like groundnut or almonds, yogurt, or yogurt with berries, hard-boiled eggs, avocado, or fruit slices. These snacks help you to maintain your blood sugar and reduce extra energy intakes.
			E 17	Eating at home, or carrying safe food when traveling ensures that you eat healthy diets that make you control your blood sugar
			E 18	Alcohol consumption can worsen diabetes-related medical complications, such as disturbances in fat metabolism, nerve damage, and eye disease. Avoid or limit alcohol to have optimal blood sugar control
Two-way messages			Month 1	Looking at the messages you have received this month, rate your confidence in selecting of healthy diets 1 2 3 4 5
			Month 2	Looking at the messages you have received this month, rate your ability to eat healthy dietary choices for diabetes care 1 2 3 4 5
			Month 3	Looking at the messages you have received this month, rate your general knowledge relating to selection and eating of health diet 1 2 3 4 5

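### Three scripted intervention texts in Table 2 (S1, S5 and E11) need a wording correction before they are sent

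*Protocol*

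**What the plan says.** Section 6.8.1 describes the intervention as a set of text messages giving practical guidance on selecting and eating a healthy diet. Table 2, printed under section 6.8.2, gives their wording. Texts labelled S concern selecting food and texts labelled E concern eating it. Four of them matter here.

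- **S1** opens with advice on meeting nutrient needs without exceeding a calorie limit, then reads: "choose a variety of nutrient-dense foods across and within all food groups in recommended amounts. Energy dense foods include vegetables, fruits, whole grains". It ends with a condition on preparation: "when prepared with little or no saturated fats, added sugars and sodium".
- **S5** names canned fruit and bottled juice as the products to avoid, and tells the participant instead to "buy fresh juice or fruits as they are energy dense and have fiber that helps in blood sugar control". It closes by noting that fresh fruit costs less.
- **E5** says "Eat fruits instead of making fruit juice", and supports this with the fiber content and slow digestion of fruit.
- **E11** says "To reduce salt intake, ensure that salt is added to food when cooking. Avoid having saltshakers on the table when eating".

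Nothing elsewhere in the Protocol corrects or qualifies these four texts.

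**The concern.** In a text-message trial the sentences sent to participants are the treatment. A slip in background prose can be ignored, but a slip in a scripted message is delivered. The three two-way messages at the end of Table 2 ask only for a rating from 1 to 5, so the script offers no point at which a puzzled participant would be put right.

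Three things look wrong. S1 uses two different terms for one list of foods. S5 carries the same term, and it presents fresh juice alongside fruit as a source of fiber for glucose control, where E5 steers people from juice to whole fruit. E11 states an aim of less salt and follows it with an instruction to make sure salt goes in. At stake is the accuracy of the advice to the 30 people planned for the intervention arm (section 6.3), in a trial that lists better food literacy as a specific objective (section 3.5).

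**Working it through.** No arithmetic applies. The check is to set the texts side by side and ask whether each can be followed as printed, alone and together with the others.

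**S1 against itself.** The first sentence asks for nutrient-dense foods under a calorie ceiling. The second lists vegetables, fruits, whole grains, beans, nuts and seeds, and lean protein, and calls them energy dense. The list can only be meant to illustrate the first sentence, so the term has been swapped. The set shows elsewhere which term was intended: E9 says "Small changes to more nutrient-dense, single food and beverage choices combine to become a nutrient dense meal". The food list and the instruction survive, and only the label is wrong. This is the clearest of the three slips.

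**S5 against S1.** S5 gives energy density as a reason to buy. That agrees with the mistaken second sentence of S1 and sits badly with its opening. It is the same slip appearing a second time and should not be counted as a separate error.

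**S5 against E5.**

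| | S5 | E5 |
|---|---|---|
| Behavior addressed | Selecting and buying | Eating |
| Compared with | Canned fruit, bottled juice | Juice made from the fruit |
| Fresh juice | Recommended, alongside fruit | Whole fruit preferred to it |
| Fiber credited to | Juice and fruit together | Fruit |

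The two can be fitted into one order: whole fruit first, fresh juice next, bottled juice last. S5 never places juice above fruit. Two differences remain. S5 offers juice as a suitable choice where E5 directs people away from it, and as its sentence is built, S5 credits juice with the fiber that E5 gives as a reason for eating the fruit. That is an inconsistency on a food that matters for blood sugar.

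**E11 against itself and against S1.** The stated aim is less salt. The instruction is to ensure that salt is added during cooking, with no *only* and no limit. Read alone, the sentence tells someone who cooks without salt to start adding it. The second sentence, on keeping the saltshaker off the table, shows that a contrast between cooking and the table was meant. E11 gives no quantity, so it can be followed together with the little-or-no-sodium condition in S1. The fault is ambiguity.

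**Texts that do not add to the case.** S12 says "Controlled portion sizes of food are important to reducing calorific intake", but it concerns portions and plate size and says nothing on fruit. E16 says of its examples "These snacks help you to maintain your blood sugar and reduce extra energy intakes", but those examples include nuts and avocado as well as fruit slices, and E16 does not call them low in energy density. E9 uses the right term without denying that a good food could be energy dense. None of the three contradicts S5.

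**Reach.** Delivery exactly as printed is not certain. Section 7.1.6 lets the monthly reply determine the type of message sent the following month. Section 6.2.2 admits readers of English or Swahili, while Table 2 is in English.

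**The case against.** The strongest reply is that this is copy-editing. The meaning of E11 is plain once both sentences are read. S1 still names the right foods and gives the right instruction. S5 argues against canned and bottled products and can be reconciled with E5. No outcome in section 6.9 measures sodium or blood pressure, and the printed food literacy questionnaire has no item on salt, energy density or juice, so the slips would be hard to see in the results.

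Most of this stands, and it rules out several stronger readings that a reader might infer:

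- *That E11 advises a higher salt intake.* Its second sentence shows otherwise.
- *That S5 and E5 give opposite instructions.* They answer different comparisons and differ in what they accept. Neither reverses the other.
- *That S12, E9 and E16 contradict S5 on energy density.* They differ from it in emphasis only.
- *That the share of affected texts measures the damage.* A proportion of messages says nothing about effect, and the count of printed texts is itself unsure, because one label in Table 2 (a second S18) appears without text.

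What the reply does not remove is that the wording is wrong or unclear as it stands, that it sits in the treatment itself, and that each slip can be corrected exactly.

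**Conclusion.** The point holds as a minor one. Three texts need correction: S1 for a wrong term, S5 for repeating that term and for recommending fresh juice as a source of fiber where E5 prefers whole fruit, and E11 for a missing *only*.

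The documents support no claim of an effect on HbA1c, on power or on the planned ANCOVA, and none is made. The conclusion rests on two assumptions: that Table 2 is the script to be loaded, and that any Swahili version is translated from it. If a corrected script already exists outside the Protocol, the point reduces to updating Table 2.

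**What to change.** Before the texts are loaded, and in every language version that will be sent:

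1. **S1:** change the label on the food list from energy dense to nutrient-dense.
2. **S5:** recommend fresh whole fruit, on the ground that it is nutrient-dense and has fiber, in place of canned fruit or any juice. The remark on cost can stay. S5 then agrees with E5.
3. **E11:** insert *only*, for example: *To cut down on salt, add it only during cooking and keep the saltshaker off the table.* No quantity limit needs to be added.

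The cost is the editing of three messages and of their translations. Whether the ethics committee must be told is an assumption, since section 7.4 lists the approvals to be sought but sets out no amendment procedure; a short notification would be prudent. Nothing changes in the design, endpoints, sample size or analysis.

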6.9 Outcomes

6.9.1 Primary outcome measures

The primary outcome measure is HbA1c which shall be measured at baseline and at the end of the intervention. HbA1c will be measured using a high-performance liquid chromatography technique using Variant II (Bio-Rad, Montreal, Quebec, Canada). FPG will be analysed by the glucose oxidase method using a Hitachi 7600 (Hitachi, Hitachi, Japan).

6.9.2 Secondary Outcome measures

Secondary outcome measures will include biochemical, anthropometric and behaviour change measurements shall be measured at baseline and endline (end of week 12). Additionally, user-satisfaction shall be assessed at 12 weeks and 24 weeks post-intervention.

Biochemical measurements will include fasting plasma Glucose (FPG), total cholesterol (TC), triglycerides (TG), and high-density lipoprotein-cholesterol (HDL-C). FPG will be analysed by the glucose oxidase method using a Hitachi 7600, while TC, TG, HDL-C will be measured using the automatic blood analyser (Hitachi 736-40). Lab testing and analysis will be conducted at the Lancet laboratories, Kenya using standard procedures.

Anthropometric measurements will include weight, height, waist and hip circumferences that shall be measured by trained research assistants, and shall follow the CDC Anthropometry Procedures Manual (104). Additionally, bioelectrical impedance analysis shall be taken to determine body fat using the

Behaviour change shall be measured by changes in dietary intake of legumes, fruits and vegetables and through the mHealth Satisfaction Questionnaire (Appendix 6). The mHealth Satisfaction Questionnaire will be adopted from the questionnaire for assessing user satisfaction with mobile health apps (105).

7 Data Collection

7.1 Quantitative Instruments

Various tools will be used to collect data. The socio-demographic and health questionnaire (Appendix 3), the food frequency questionnaire (Appendix 4) and the self-perceived food literacy questionnaire (Appendix 5) will be administered on all participants after enrolment. The socio-demographic and health questionnaire and the food frequency questionnaires have been piloted and used in studies in Kenya, while the self-perceived food literacy questionnaire shall be piloted during the study. These tools will be administered by trained research personnel in either Swahili or English, depending on the preference of the participant.

7.1.1 *Socio-demographic and health history questionnaire*

This study will utilize the electronic socio-demographic and health history questionnaire (Appendix 4) that was previously used in a sister study conducted in Makueni County, Kenya (Protocol number AMREF P424 2018). The questionnaire was developed based on the World Health Organization STEPS Instrument and Support Materials (106) and piloted in Makueni County, Kenya.

7.1.2 *Self-perceived food literacy questionnaire*

The self-perceived food literacy questionnaire is based on the tool used to assess the food literacy among people with chronic diseases in Netherlands (107). This tool was developed through an expert-based and theory-driven process and shall be piloted and adjusted before being used in the Kenyan settings. The responses options are a 5-point Likert scale where 1= 'not at all/never' to 5='yes/always' (Appendix 4).

7.1.3 *Anthropometric measurements*

Anthropometric measurements will be taken during the filling of the socio-demographic and Health history questionnaire. These measurements will include height, weight waist and hip circumference. Height and weight shall be used to calculate the body mass index (BMI).

7.1.4 *Body composition*

Body composition of all participants shall be taken at baseline and at the end of the intervention. The measurements shall be conducted by trained research assistants using the *Bodystat 500*[®] Body Composition Monitor.

7.1.5 *Blood samples*

Two trained phlebotomists, each serving one hospital, will draw 5 ml venous blood using the closed vacuum extraction tubes with single-use needle and needle holder and following the WHO and Kenya Medical and Research Institute (KEMRI) guidelines(108). Laboratory requisition forms indicating the participant identification code shall be written for all the collected samples. The samples will be immediately stored in insulated coolers containing ice/cold packs at around 4°C. At the end of sample collection, the phlebotomists will centrifuge the blood samples and serum transferred into sterile cryo-vials in the two level 4 hospital laboratories. Two centrifuges shall be provided by the study, assigned to the two study phlebotomists. Thereafter the samples will be frozen at -20 degrees centigrade in study nitrogen tanks and transported to Lancet Laboratories[®] in Nairobi for analysis.

Phlebotomists will ensure hand hygiene by using pair of well-fitting clean disposable latex-free gloves, alcohol rubs, water and soap before after each blood draw to reduce risks of cross-contamination. Sufficient single-use disposable needles and sampling tubes will also be ensured for each blood sampling.

The study shall provide all required laboratory disposal equipment and materials.

Disposal of all lab waste will adhere to Laboratory Biosafety and Bisecurity Policy Guidelines (109). In brief the following measures shall be ensured in disposal of infectious wastes:

- i. Red infectious/biohazard waste disposal containers shall be located in each area of the laboratory where infectious waste may accumulate.
- ii. Containers shall be lined with disposable bright orange/red biohazard bags before placing infectious waste into them to prevent leakage.
- iii. Infectious waste containers shall not be filled more than three-quarters full.
- iv. Biohazard bags shall be removed from the work area after each day's use.
- v. Bags and containers shall be transport to the biohazard holding room as per the facility procedures.

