10.4 Budget

The total budget for the entire study is estimated to cost Kes 2,550,320 as tabulated below

Table 5. Budget

Ethics Review Fees and Research Permit				
Item	Units	Unit Cost	Frequency	Total Cost (Ksh)
AMREF Ethics review	1	5000	1	5,000
NACOSTI Research Permit	1	2000	1	2,000
Sub total				7,000
Mobilization and planning				
Item	Units	Unit Cost	Days	Total Cost
Community Mobilizer	6	2,540	1	15,240
Airtime for mobilization	6	500	4	12,000
Sub total				27,240
Lab test Equipment				
Item	Units	Unit Cost	Frequency	Total Cost
Plain Tubes for Serum Zinc Collection	2	1,200	1	2,400
Vacutainer needles (100pcs) Gauge 21	2	1,400	2	5,600
Alcohol swabs (100pcs)	1	420	2	800
Micro pore Tape	1	400	1	400
Disposable Rubber Gloves (Dust free 100pcs)	1	1,000	2	2,000
Test Strips for Cholesterol Metre (25pcs)	5	2,500	2	25,000
Test Strips for Glucometer (50pcs)	3	1,600	2	9,600
Biohazard Safety Box	1	300	1	300
Red Disposable bags (Big)	5	50	1	250
Red Disposable bags (small))	10	30	1	300
Hand Sanitizers (500ml)	5	500	1	2,500
Mask (50pcs)	5	800	1	4,000
Cryol Vial (100pcs)	3	1,000	1	3,000
Sub total				56,150
Equipment for Handling, Transfer and Storage of Blood Samples				
Item	Units	Unit Cost	Frequency	Cost
Refill of Nitrogen Tank with liquid nitrogen 47lit	47	480	1	22,560
Sub total				22,560
Stationery Costs				
Item	Units	Unit Cost	Frequency	Cost
Printing paper	5	500	2	5,000
Pens	15	15	2	450
Sub total				5,450
Lab test costs				
Item	Pts	Unit Cost	Frequency	Cost
HbA1C	60	2949	3	530,820
Lipid Profile	60	2949	3	530,820
Total Cholesterol, Serum	60	949	3	170,820
Sub total				1,232,460
mHealth Costs				

Item	Pts	Unit Cost	Frequency	Cost
Setting up Charges	-	20,000	1	20,000
Maintenance Costs	-	20,000	1	20,000
Bulk SMS Services: Intervention Arm	30	5	48	7,200
Bulk SMS Services: Control Arm	30	5	4	600
Audio Calls: Intervention	30	5	12	18,000
Sub total				65,800
Study monitoring				
Item	Pax	Unit Cost	Frequency	Cost
Per Diem (Principal Investigator)	1	7,640	20	152,800
Per Diem (PhD researcher)	1	7,640	30	229,200
Per Diem (Driver)	1	5,135	30	154,050
Sub total				536,050
Personnel				
Item	Pax	Stipend	Days	Cost
Phlebotomist	2	7,640	14	213,920
Enumerators	4	2,540	14	142,240
Enumerator's transport	6	1,000	2	12,000
Research Assistant	1	795	90	71,550
Community Mobilization	2	2,540	14	71,120
Sub total				510,830
Transport				
Item	Cars	Unit Cost	Frequency	Cost
Fuel Costs	1	10,000	2	20,000
Sub total				20,000
Grand Total				2,483,540

11 References

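### The glucose outcome is defined as fasting plasma glucose, but the only blood-handling route keeps serum and sets no time limit to centrifugation

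*Protocol*

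**What the plan says.** **Outcome.** Section 6.9.2 lists FPG among the biochemical secondary outcomes, at baseline and week 12. The list of acronyms expands FPG as plasma glucose. The assay is fixed: "FPG will be analysed by the glucose oxidase method using a Hitachi 7600". Section 6.9.1 repeats it beside HbA1c. On location, section 6.9.2 says: "Lab testing and analysis will be conducted at the Lancet laboratories, Kenya using standard procedures".

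**Handling.** Section 7.1.5 is the only account of how blood is taken and processed:
- The draw is described as follows: "Two trained phlebotomists, each serving one hospital, will draw 5 ml venous blood using the closed vacuum extraction tubes".
- The tubes are then cooled: "The samples will be immediately stored in insulated coolers containing ice/cold packs at around 4°C".
- Separation follows, and here the protocol names the fraction that is kept: "At the end of sample collection, the phlebotomists will centrifuge the blood samples and serum transferred into sterile cryo-vials".

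The centrifuging is done in the two hospital laboratories. The samples are then frozen and sent to Nairobi. The section mentions no plasma aliquot, no anticoagulant or glycolysis inhibitor, and no limit on the time between draw and separation.

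**Budget.** In section 10.4 the only blood tube itemised is "Plain Tubes for Serum Zinc Collection". The table also lists glucometer strips. Its laboratory test lines are HbA1c, lipid profile and total cholesterol; no laboratory glucose test is costed.

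**The concern.** Two things do not fit together. First, the outcome is a plasma measurement, but the stated procedure retains serum. A team that followed section 7.1.5 exactly would have no plasma to send. This is a conflict between two statements in the protocol, not a detail left for a later document.

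Second, blood cells go on consuming glucose until they are separated. Cooling slows this but does not stop it. With no time limit, the wait can differ between participants, between the two hospitals and between a participant's baseline and week-12 visits. Any loss lowers the measured value, and a varying loss adds error to the change from baseline.

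FPG is the only glycaemic outcome besides HbA1c, so a reader of the results is likely to set the two side by side. Section 6.3 also says that the study is meant to supply parameters for a fully powered trial. It does not name FPG there, but any glucose mean and SD carried forward would contain this error. Baseline specimens cannot be taken again later.

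**Working it through.** The protocol gives no figure to reproduce: no loss rate, no waiting time and no power for FPG. The check is a comparison of passages followed by a sensitivity calculation.

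**1. Specimen named against specimen kept**

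| Item | Outcome sections (6.9.1, 6.9.2) | Handling (7.1.5) | Budget (10.4) |
|---|---|---|---|
| Fraction | Plasma | Serum only | Plain serum tubes |
| Glucose method | Glucose oxidase, laboratory analyser | Frozen serum sent to the central laboratory | 3 × 50 × 2 = 300 glucometer strips; no laboratory glucose test |
| Time to separation | Not stated | When sample collection ends; no maximum | Not applicable |

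The plasma/serum mismatch holds however the timing phrase is read.

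**2. How long a wait is plausible**

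Section 6.4 gives 15 per arm in each of two hospitals: 2 × 2 × 15 = 60 participants. The budget pays two phlebotomists for 14 days, or 28 phlebotomist-days.
- If those days cover one round of sampling: 60 / 28 = 2.1 draws per phlebotomist-day.
- If they cover the three rounds costed for laboratory tests: 180 / 28 = 6.4.

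A variable wait is therefore possible, but its length cannot be derived, and large daily batches are not indicated.

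**3. Size of a possible loss**

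All inputs here are assumptions: true glucose 9 mmol/L, loss rate r per hour, and wait uniform from 0 to T hours (one spin at the end of a session of length T).
- Mean loss = 9 × [1 − (1 − e^(−rT)) / (rT)]
- Gap between first and last participant drawn = 9 × (1 − e^(−rT)); the first waits longest
- Added SD ≈ gap / √12

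| r per hour | T = 2 h: mean loss; gap | T = 6 h: mean loss; gap; added SD |
|---|---|---|
| 0.5% | 0.04; 0.09 | 0.13; 0.27; 0.08 |
| 1% | 0.09; 0.18 | 0.26; 0.52; 0.15 |
| 2% | 0.18; 0.35 | 0.52; 1.02; 0.29 |
| 5% | 0.44; 0.86 | 1.22; 2.33; 0.67 |

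All values are in mmol/L. The 5% row stands for slow or poor cooling and fits badly with immediate chilling, so the upper rows are the more plausible ones. With no loss, every entry is zero.

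**4. Effect on precision**

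Take an assumed between-person SD of 1.5 to 3 mmol/L and the added SD of 0.29 (2% per hour, 6 h):
- √(1.5² + 0.29²) / 1.5 = 1.019, an inflation of about 2%
- √(3² + 0.29²) / 3 = 1.005, about 0.5%

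In this case the added noise at a single visit is minor.

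**The case against.** The case on the other side is substantial.

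- **Chilling.** Samples go onto ice or cold packs immediately, so any loss may be small. This stands, and it is why the size must be called unknown.
- **Timing.** The centrifuging phrase may mean the end of each person's draw, not the end of the session. The holding step in coolers and the later spin in the hospital laboratory favour the session reading, but the text does not settle it. On the other reading the wait shrinks to little more than clotting time, and only the specimen mismatch is left.
- **Arm comparison.** A reader might infer that the wait would create a false glucose difference between arms, since the trial is unblinded (section 6.7) and no draw order is set. The documents do not support that. Both arms are allocated within each hospital and share one phlebotomist and one procedure, so a common loss largely cancels. Nothing indicates that one arm is drawn earlier.
- **Budget.** A reader might take the absence of an inhibitor tube from the budget as proof that none will be used. It is weak evidence. The listed tubes are labelled for zinc, which is not an outcome here. No HbA1c tube is listed either, and section 7.1.5 undertakes to supply enough tubes.
- **Role of FPG.** The abstract's list of secondary outcomes omits it, and section 8.2 specifies ANCOVA only for HbA1c. This limits the importance of the point.
- **Other routes and guidance.** The glucometer strips cannot be the intended source of FPG, because sections 6.9.1 and 6.9.2 fix a laboratory assay. The reference to standard procedures concerns testing at the central laboratory. The guidelines cited in section 7.1.5 are attached to drawing blood, and whether they cover glucose handling cannot be seen here. None of this removes the conflict on the specimen.

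**Conclusion.** The point holds as a conflict between sections. The protocol names plasma glucose, and its only handling route keeps serum without a time limit to separation. That conclusion needs no assumption.

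The effect on the values is a possibility, not a result. A reader might conclude that FPG will be materially biased low; the documents do not establish this, because they give neither a loss rate nor a wait and they specify immediate chilling. Under assumed rates of 0.5 to 2% per hour and sessions of 2 to 6 hours, the mean fall from an assumed 9 mmol/L runs from 0.04 (negligible) to 0.52 mmol/L. The likely consequence is an uncertain level and some added noise across participants, hospitals and visits. A biased arm comparison would require waits that differ by arm.

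For a secondary outcome this should be corrected, and it should be done before baseline sampling. It is separate from the question of which specimen serves HbA1c: a whole-blood tube for HbA1c would not settle glucose.

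**What to change.** In section 7.1.5, give glucose its own route:
- take part of the same 5 ml into a glycolysis-inhibitor tube;
- centrifuge within a fixed maximum time of each participant's draw;
- store a separate plasma aliquot for FPG, and keep serum for the lipids;
- record draw and spin times on the existing requisition form.

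If the sponsor prefers to keep serum only, rename the outcome serum glucose throughout and do not report it as FPG. A time limit to separation would still be worth stating.

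In either case, reconcile sections 6.9.1, 6.9.2, 7.1.5 and 10.4 before baseline sampling. This includes stating what the glucometer strips are for and costing a laboratory glucose test if one is intended. Section 8.2 should use the same name for the measurement; it now uses the abbreviation FBG, which the list of acronyms does not contain.

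The cost is about 60 extra tubes per visit and slightly more work for the phlebotomists, including earlier or more frequent spins on the two centrifuges already provided. No extra venepuncture, participants or staff are needed. If a laboratory glucose test has not been budgeted elsewhere, its price is an additional cost that the protocol does not give.
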